5.4. Withdrawal/Stopping Criteria

The following actions must be taken in relation to a subject who fails to attend the clinic for a required study visit:

- The site must attempt to contact the subject and re-schedule the missed visit as soon as possible.
- The site must counsel the subject on the importance of maintaining the assigned visit schedule and ascertain whether or not the subject wishes to and/or should continue in the study.
- In cases where the subject is deemed 'lost to follow up', the investigator or designee must make every effort to regain contact with the subject (where possible, 3 telephone calls and if necessary a certified letter to the subject's last known mailing address or local equivalent methods). These contact attempts should be documented in the subject's medical record.
- Should the subject continue to be unreachable, only then will he/she be considered to have withdrawn from the study with a primary reason of "Lost to Follow-up".

Non-compliance to the study regimen or withdrawal of consent (no reason has to be given by the individual subject) will lead to the removal from the study. An individual subject may withdraw from study treatment at any time at his/her own request, or may be withdrawn at any time at her own request, or at the discretion of the investigator for safety, behavioural or administrative reasons. If a subject withdraws from the study, he/she may request destruction of any samples taken, and the investigator must document this in the site study records. The entire study will be terminated if the sponsor (GSK) stops the study at any stage.

Individual subjects may be withdrawn at the investigator's discretion at any time during the study, provided there is a valid and confirmable clinical reason. The presence of severe AEs predefined as stopping criteria below in Section 5.5, or SAE as defined in [Appendix 3](#), will lead to the withdrawal of an individual subject. Withdrawn subjects will be replaced by new subjects as per the guidance in Section 6.4

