5.4.2. Liver Chemistry Stopping Criteria

Liver chemistry stopping and increased monitoring criteria have been designed to assure subject safety and evaluate liver event etiology (in alignment with the FDA premarketing clinical liver safety guidance).

<http://www.fda.gov/downloads/Drugs/GuidanceComplianceRegulatoryInformation/Guidances/UCM174090.pdf>

Study treatment will be discontinued **for a healthy volunteer subject in Part A or B, or a systemic amyloidosis patient without liver involvement /no biochemical liver dysfunction in Part C** with baseline liver chemistry within the normal reference range for ALT if they are reasonably attributable to GSK3039294 and provided the following liver chemistry stopping criteria are met:

Phase I Liver Chemistry Stopping Criteria – Liver Stopping Event Algorithm

In Part C, systemic amyloidosis patients will be required to return for follow-up liver chemistry assessments within 1 week of the changes from the baseline liver chemistry at Day -1 (see [Table 6](#)) being reported. Individual systemic amyloidosis patients will be withdrawn from the study if the following liver chemistry changes are reported from baseline at Day -1 (see [Table 6](#)).

Table 6 Change from baseline in liver chemistry for repeat or withdrawal

Baseline Liver Chemistry	Repeat assessment within 1 week	Withdrawal
x1 ULN < ALT ≤ x3 ULN Bilirubin ≤ x1ULN	ALT > x4 ULN Bilirubin > x 1.5 ULN	ALT > x6 ULN Bilirubin > x 1.5 ULN
x1 ULN < ALT ≤ x3 ULN Bilirubin ≤ x1.5 ULN	ALT > x4 ULN Bilirubin > x 2 ULN	ALT > x6 ULN Bilirubin > x 2 ULN

Liver Safety Required Actions and Follow up Assessments Section can be found in [Appendix 2](#) (Section 12.2)

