
 • Immediately discontinue study treatment • Report the event to GSK within 24 hours • Complete the liver event CRF, and complete an SAE data collection tool if the event also meets the criteria for an SAE² • Perform liver event follow up assessments • Monitor the subject until liver chemistries resolve, stabilise, or return to within baseline (see MONITORING below) • Do not restart/rechallenge subject with study treatment. Permanently discontinue study treatment and may continue subject in the study for any protocol specified follow up assessments 
MONITORING:
 
If ALT\geq3xULN AND bilirubin \geq 2xULN or INR >1.5:
 
 • Repeat liver chemistries (include ALT, AST, alkaline phosphatase, bilirubin) and perform liver event follow up assessments within 24 hrs • Monitor subjects twice weekly until liver chemistries resolve, stabilise or return to within baseline • A specialist or hepatology consultation is recommended 
If ALT\geq3xULN AND bilirubin < 2xULN and INR \leq1.5:
	
 • Viral hepatitis serology³ • Blood sample for pharmacokinetic (PK) analysis, obtained within 48 hours of last dose⁴ • Serum creatine phosphokinase (CPK) and lactate dehydrogenase (LDH). • Fractionate bilirubin, if total bilirubin\geq2xULN • Obtain complete blood count with differential to assess eosinophilia • Record the appearance or worsening of clinical symptoms of liver injury, or hypersensitivity, on the AE report form • Record use of concomitant medications on the concomitant medications report form including acetaminophen, herbal remedies, other over the counter medications. • Record alcohol use on the liver event alcohol intake case report form 
If ALT\geq3xULN AND bilirubin \geq 2xULN or INR >1.5:
 
 • Anti-nuclear antibody, anti-smooth muscle antibody, Type 1 anti-liver kidney microsomal antibodies, and quantitative total immunoglobulin G (IgG or gamma globulins).

Liver Chemistry Stopping Criteria – Liver Stopping Event	

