
 • Repeat liver chemistries (include ALT, AST, alkaline phosphatase, bilirubin) and perform liver event follow up assessments within 24-72 hrs • Monitor subjects weekly until liver chemistries resolve, stabilize or return to within baseline 	
 • Serum acetaminophen adduct HPLC assay (quantifies potential acetaminophen contribution to liver injury in subjects with definite or likely acetaminophen use in the preceding week [James, 2009]). NOTE: not required in China • Liver imaging (ultrasound, magnetic resonance, or computerised tomography) and /or liver biopsy to evaluate liver disease: complete Liver Imaging and/or Liver Biopsy CRF forms.

1. Serum bilirubin fractionation should be performed if testing is available. If serum bilirubin fractionation is not immediately available, discontinue study treatment for that subject if ALT \geq 3xULN **and** bilirubin \geq 2xULN. Additionally, if serum bilirubin fractionation testing is unavailable, **record presence of detectable urinary bilirubin on dipstick**, indicating direct bilirubin elevations and suggesting liver injury.
2. All events of ALT \geq 3xULN and bilirubin \geq 2xULN (>35% direct bilirubin) or ALT \geq 3xULN and INR > 1.5, if INR measured, which may indicate severe liver injury (possible 'Hy's Law'), must be reported as an SAE (excluding studies of hepatic impairment or cirrhosis); INR measurement is not required and the threshold value stated will not apply to subjects receiving anticoagulants
3. Includes: Hepatitis A IgM antibody; Hepatitis B surface antigen and Hepatitis B Core Antibody (IgM); Hepatitis CRNA; Cytomegalovirus IgM antibody; Epstein-Barr viral capsid antigen IgM antibody (or if unavailable, obtain heterophile antibody or monospot testing); Hepatitis E IgM antibody
4. PK sample may not be required for subjects known to be receiving placebo or non-GSK comparator treatments. Record the date/time of the PK blood sample draw and the date/time of the last dose of study treatment prior to blood sample draw on the CRF. If the date or time of the last dose is unclear, provide the subject's best approximation. If the date/time of the last dose cannot be approximated OR a PK sample cannot be collected in the time period indicated above, do not obtain a PK sample. Instructions for sample handling and shipping are in the SRM

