
f. Other situations:
 
 • Medical or scientific judgment should be exercised in deciding whether reporting is appropriate in other situations, such as important medical events that may not be immediately life-threatening or result in death or hospitalization but may jeopardize the subject or may require medical or surgical intervention to prevent one of the other outcomes listed in the above definition. These should also be considered serious. • Examples of such events are invasive or malignant cancers, intensive treatment in an emergency room or at home for allergic bronchospasm, blood dyscrasias or convulsions that do not result in hospitalization, or development of drug dependency or drug abuse

g. Is associated with liver injury and impaired liver function defined as:
 
 • ALT \geq 3xULN and total bilirubin* \geq 2xULN (>35% direct), or • ALT \geq 3xULN and INR** > 1.5. 
* Serum bilirubin fractionation should be performed if testing is available; if unavailable, measure urinary bilirubin via dipstick. If fractionation is unavailable and ALT \geq 3xULN and total bilirubin \geq 2xULN, then the event is still to be reported as an SAE.
 
** INR testing not required per protocol and the threshold value does not apply to subjects receiving anticoagulants. If INR measurement is obtained, the value is to be recorded on the SAE form.

 • Refer to Appendix 2 for the required liver chemistry follow-up instructions

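### For Part C patients entering with ALT above 1 and up to 3×ULN, Table 6, Appendix 2 and the SAE rule give conflicting mandatory liver stopping instructions

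*Protocol*

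**What the plan says.** Section 5.1 admits patients with ALT up to and including 3×ULN, among them some with a large amyloid load in the liver. Four places then govern an abnormal liver result in Part C.

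- **Section 5.4.2, opening text.** The stopping algorithm covers healthy volunteers and amyloidosis patients without liver dysfunction, "with baseline liver chemistry within the normal reference range for ALT".
- **Section 5.4.2, Table 6.** Both rows have baseline ALT above 1 and up to 3×ULN. Row 1 (baseline bilirubin ≤1×ULN) lists ALT >4 and bilirubin >1.5 under the column "Repeat assessment within 1 week", and ALT >6 and bilirubin >1.5 under withdrawal. Row 2 (baseline bilirubin ≤1.5×ULN) lists ALT >4 and bilirubin >2 for the repeat, and "ALT > x6 ULN Bilirubin > x 2 ULN" for withdrawal. No connector is printed. The section then refers to Appendix 2 for required actions.
- **Appendix 2, 12.2.2 (Patients).** ALT ≥3×ULN is a liver stopping event: "Immediately discontinue study treatment", permanently, although the patient may remain for follow-up. If bilirubin is also ≥2×ULN, or INR is >1.5, the site must repeat the chemistries and "perform liver event follow up assessments within 24 hrs". With ALT ≥3×ULN, either bilirubin ≥2×ULN (>35% direct) or INR >1.5 is a possible Hy's Law event that "must be reported as an SAE (excluding studies of hepatic impairment or cirrhosis"). This is not such a study.
- **Sections 12.4.2(g) and 5.4.** Item (g) repeats that SAE definition. If bilirubin cannot be fractionated, "then the event is still to be reported as an SAE". Section 5.4 says an SAE "will lead to the withdrawal of an individual subject", but cites Appendix 3, which is the genetics appendix. The SAE definition is in Appendix 4.

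No text says which rule prevails.

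**The concern.** Table 6 appears to exist so that patients who start with raised ALT are not stopped at the limit used for people with normal ALT. Appendix 2, under a heading that covers all patients, applies that lower limit to them anyway. For the most serious pattern, ALT and bilirubin raised together, the site can find a 1-week repeat in one place and immediate discontinuation, a 24-hour repeat and withdrawal in others.

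The stake is the safety of individual patients in a group selected partly for liver involvement. Table 6 does not suspend dosing while the repeat is awaited, and 1 week is up to 7 of the 21 dosing days. Classification also matters beyond the patient: under Section 5.5 an SAE attributed to study drug halts dosing in the whole study until a safety review.

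**Working it through.** There is no plan figure to reproduce. The check applies each rule to the same results (all values in ×ULN; baseline ALT 2; direct bilirubin >35% of total).

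| Result | Table 6, AND | Table 6, OR | 12.4.2(g) with 5.4 | Appendix 2 as headed |
|---|---|---|---|---|
| ALT 3.5, bilirubin 1.0 | no step | no step | not an SAE under (g) | discontinue |
| ALT 5, bilirubin 1.0 | no step | repeat within 1 week | not an SAE under (g) | discontinue |
| ALT 8, bilirubin 1.0 | no step | withdraw | not an SAE under (g) | discontinue |
| ALT 3.5, bilirubin 2.5 | no step | withdraw | withdraw | discontinue, repeat within 24 h |
| ALT 5, bilirubin 2.5 | repeat within 1 week | withdraw | withdraw | discontinue, repeat within 24 h |
| ALT 5, bilirubin 2.0, row 2 | no step | repeat within 1 week | withdraw | discontinue, repeat within 24 h |

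**Step 1, independent of the connector.** Appendix 2 stops at ALT ≥3. Table 6 first acts on ALT above 4. Any patient reaching 4 or 6 has already met the Appendix 2 stop. Eligibility allows ALT ≤3 and the stop is ALT ≥3, so a patient admitted at exactly 3.0 meets it at baseline. The first two table lines show the mismatch under either connector.

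**Step 2, by connector.** Take ALT at 3, 3.5, 4, 4.5, 5, 6, 6.5 and 8, and bilirubin at 1, 1.6, 2, 2.1, 2.5, 3 and 5. That gives 8 × 7 = 56 results, of which 8 × 5 = 40 have ALT ≥3 and bilirubin ≥2. Of those 40:

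- AND, row 1: the six ALT values up to 6 are not withdrawn, 6 × 5 = 30. At ALT 3 to 4 (3 × 5 = 15) there is not even a repeat.
- AND, row 2: the same 30, plus ALT 6.5 and 8 at bilirubin exactly 2, because Table 6 uses >2 where the SAE rule uses ≥2. Total 32.
- OR, row 1: 0 missed.
- OR, row 2: 6 missed, all at bilirubin exactly 2 with ALT ≤6.

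These counts map the rules; they are not frequencies of patients.

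**Step 3, which connector is likelier.** The two baseline conditions in each row can only be joint. The bilirubin limit is the same in the repeat and withdrawal columns, so under OR a bilirubin value that calls for a repeat always calls for withdrawal too. Both features favour AND, but neither proves it.

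**Step 4, if Appendix 2 is confined to normal baseline ALT.** This follows Section 5.4.2's opening text and removes the conflict in Step 1. Under AND it leaves raised-ALT patients with no ALT-alone stop (third line of the table). The SAE rule has no baseline limit, so the conflict with withdrawal in Step 2 remains.

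**The case against.** The strongest reply is that stopping criteria are cumulative. A blank in Table 6 is not permission to continue. Section 5.4 withdraws for an SAE, Appendix 2 discontinues, restart is barred, and the investigator may withdraw anyone for a valid clinical reason. This stands against a stronger reading that a reader might infer, namely that the protocol keeps a possible Hy's Law patient on drug. Taken as a whole it does not. What remains is that mandatory texts order different actions and no precedence is given.

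Second, the table was read from a PDF, so the AND is an inference, and OR nearly closes the Hy's Law gap. That also stands. A reader might go further and say that neither connector makes the table work. The documents do not support this: nothing says a withdrawn patient is not re-tested, so equal bilirubin limits under OR could mean withdraw and repeat.

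Third, a finding tied to the amyloidosis and no worse than expected is not an AE under 12.4.1, and so not an SAE. This limits the SAE route but does not lift the Appendix 2 treatment stop.

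Fourth, the impact is bounded. Outpatient visits appear to fall at about Days 12, 15, 18 and 21, so a retest may come well before 7 days. The patient who meets the stop at baseline is a single boundary value.

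**Conclusion.** The concern holds as a conflict between mandatory instructions for Part C patients with baseline ALT above 1 and up to 3×ULN.

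- **Under either connector:** Appendix 2's stop at ALT ≥3×ULN pre-empts Table 6's 4× and 6×ULN limits. This assumes Appendix 2 applies to all patients, as its heading says.
- **Under AND:** for ALT 3 to 6×ULN with bilirubin ≥2×ULN, Table 6 gives at most a 1-week repeat where other sections require withdrawal or immediate discontinuation. ALT above 6×ULN with normal bilirubin gets no Table 6 action.
- **Under OR:** the Hy's Law gap is only bilirubin exactly 2.0×ULN in row 2 with ALT ≤6×ULN.

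The SAE comparison assumes direct bilirubin >35%, or fractionation unavailable, and an event that counts as an AE. The protocol does not say how many of the minimum 12 Part C patients will have raised baseline ALT. Sample size and inference are unaffected. The point should be corrected because it is a written safety rule and the correction is cheap.

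**What to change.** Amend the liver rules for baseline ALT above 1 and up to 3×ULN, using limits the protocol already contains:

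1. Print the connector in Table 6.
2. Add a stand-alone line: discontinue and withdraw at ALT ≥3×ULN with bilirubin ≥2×ULN (>35% direct, or fractionation unavailable), or with INR >1.5 if measured, with Appendix 2's repeat within 24 hours.
3. Withdraw at ALT >6×ULN at any bilirubin.
4. Repeat within 1 week for any ALT >4 to ≤6×ULN that does not meet withdrawal, whatever the bilirubin or direct fraction. This keeps a step for a result such as ALT 5, bilirubin 2.5, direct 30%, which Table 6 under AND would repeat.
5. If OR was intended, keep the bilirubin-alone withdrawal limits (>1.5×ULN in row 1, >2×ULN in row 2).
6. Limit Appendix 2's ALT-alone stop at ≥3×ULN to patients with normal baseline ALT, in line with Section 5.4.2.
7. In Section 5.4, change the SAE reference from Appendix 3 to Appendix 4.

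The cost is one table, one scope sentence and one cross-reference in an amendment, with no scheduled visits added. A few more patients with raised baseline ALT may be withdrawn or re-tested than under Table 6 alone. Item 6 relaxes Appendix 2 as now headed, so the sponsor should confirm that this is the intent.

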5.4.2.1. Study Treatment Restart or Rechallenge

Study treatment restart or rechallenge after liver chemistry stopping criteria are met by any subject participating in this study is not allowed.

5.4.3. QTc Stopping Criteria

Healthy Volunteers & Amyloidosis Patients:

A healthy volunteer or patient that meets either bulleted criterion below will be withdrawn from the study.

- QTcF > 500 msec,
- Change from baseline in healthy volunteer subjects: QTcF >60 msec

For patients with underlying **bundle branch block**, follow the discontinuation criteria listed below:

Baseline QTcF with Bundle Branch Block	Discontinuation QTcF with Bundle Branch Block
< 450 msec	> 500 msec
450 – 480 msec	≥ 530 msec

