Safety, PK and PD data will be reviewed on an ongoing basis throughout the study by the study team and investigator in order to inform dosing decisions for subsequent dosing sessions, cohorts and study parts.

In addition, in all Parts of the study, individual profiles over time will also be presented graphically for selected urine and plasma laboratory parameters pertaining to the kidney. To inform dosing decisions for subsequent dosing sessions in Part A, individual values of C_{max} and AUC_[0-inf] will be derived by means of non-compartmental analysis. To inform dosing decisions for subsequent study parts, GSK2315698 concentration data and plasma SAP levels will be analysed using the PK/PD model that was developed for GSK2315698.

Primary and secondary analyses

Safety, PK and PD data will be listed, summarised and presented graphically as appropriate. GSK2315698 concentration data and plasma SAP levels will be analysed using the PK/PD model that was developed for GSK2315698.

Cohort Safety Reviews: A safety review will be performed on completion of each Cohort in Part B, as well as at completion of Cohort 5 in Part C (see Section 4.2.2. & Section 4.2.3.). Initiation of Cohort 4a will be contingent on the findings of the safety review at completion of Cohort 3 (see Section 4.2.2.)

Summary of Cardiac Arrhythmia Adverse Events in Part A of this study

A total of 4 separate arrhythmias in 3 male subjects over 45 year old were reported on 24-hour Holter after single dose administration of GSK3039294 in Part A. Three episodes of supraventricular tachycardia (SVT), all of atrial tachycardia morphology at doses of GSK3039294 at 600mg and 1200mg, and one episode of a single 5-beat accelerated idioventricular rhythm (AIVR) at 600mg GSK3039294, were reported in these 3 separate subjects. Each of the events was of short duration, completely asymptomatic, and was not associated with hemodynamic instability.

No prolongation of the QTcF interval was observed in any subject after administration of 200mg, 600mg, or 1200mg of GSK3039294 in Part A.

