1. Current or chronic history of liver disease, or known hepatic or biliary abnormalities (with the exception of Gilbert's syndrome or asymptomatic gallstones)
2. QTcF > 450 msec from a mean of triplicate readings triplicate readings taken 5 minutes apart

Additional Exclusion Criteria – Patients

[1] CONCURRENT CONDITIONS/MEDICAL HISTORY (INCLUDES LIVER FUNCTION AND QTc INTERVAL)

1. Non-amyloid heart diseases (e.g. epicardial coronary artery heart disease, or non-amyloid valvular heart disease)
2. Subject with mean QTcF of >480ms from a mean of triplicate readings
3. **Cardiac Amyloidosis Patients ONLY** – Within 3 months of Screening, *Or* at Screening: **a).** Sustained (≥ 10 beats) / symptomatic monomorphic ventricular tachycardia (VT), or rapid polymorphic VT; **b).** Complete heart block; **c).** Brady arrhythmias deemed clinically concerning in this patient population by the Investigator in consultation with the Medical Monitor
4. Plasma albumin < 30g/litre

5. A syncopal episode, within 4 weeks of screening
6. Average SBP \leq 100mmHg at Screening from triplicate readings in Part C systemic amyloidosis patients with known cardiac amyloid involvement *Or*, Average SBP \leq 90mmHg at Screening from triplicate readings in systemic amyloidosis patients *without* known cardiac amyloid involvement
7. Implantable cardiac defibrillator (ICD)
8. Insertion of permanent pacemaker in last 2 months
9. Decompensated or uncontrolled heart failure in last 2 months
10. Anaemia Hb $<$ 9g/dL
11. Uncontrolled hypertension in a known hypertensive patient, or fulfilling diagnostic criteria of essential hypertension at screening
12. Presence of any co-morbid condition (e.g. severe or unstable coronary artery disease; moderate to severe chronic obstructive pulmonary disease) which in the opinion of the investigator would increase the potential risk to the subject
13. Non-amyloidosis causes of chronic liver disease (with the exception of Gilbert's syndrome or clinically asymptomatic gallstones)
14. Diabetes Mellitus
15. Glycosuria at Screening
16. Urine pH $<$ 6.0 at screening
17. Hypoalbuminaemia ($<$ 30nmol/L)
18. Hypophosphatemia (less than 0.8mmol/L)
19. Prothombin time $>$ 1.5xULN
20. Malabsorption syndrome of any aetiology

[2] CONCOMITANT MEDICATIONS

1. Compassionate use of CPHPC or participation in a separate clinical trial involving CPHPC within 3 months of screening

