5.4.1. Cardiovascular Safety Stopping Criteria

1. New onset or worsening symptoms of cardiac ischemia which is reasonably attributable to GSK3039294
2. Development of decompensated or uncontrolled cardiac failure which is reasonably attributable to GSK303294.
3. Systolic blood pressure > 170 mmHg as an average of triplicate readings taken at rest over 15 minutes on three consecutive days at any time after administration and is reasonably attributable to GSK3039294.
4. **Healthy Volunteers & Amyloidosis Patients without bundle branch block:** QTcF > 500 msec, (or a change from baseline of QTcF > 60 msec on a 12-lead

ECG in healthy volunteers) which is reasonably attributable to GSK3039294 on an average from triplicate readings (see Section 5.4.3).

5. **Systemic Amyloidosis patients with bundle branch block** - if baseline QTcF < 450 msec: QTcF > 500 msec on a 12-lead ECG at any time after administration of GSK3039294; If baseline QTcF 450-480 msec: QTcF > 530 msec at any time after drug administration and is reasonably attributable to GSK3039294, as an average of triplicate readings (see Section 5.4.3).
6. Any cardiovascular SAE as predefined in [Appendix 4](#) after drug administration and is reasonably attributable to GSK3039294

Please also see Section 5.4.4. Cardiac Arrhythmia stopping criteria

[figure not shown]

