7.3.4. Vital Signs

- Vital signs will be measured in semi-supine position after 5 minutes rest and will include temperature, systolic and diastolic blood pressure and pulse.
- Triplicate readings of blood pressure and pulse rate will be taken and averaged at all times.

7.3.5. Cardiac Monitoring – Electrocardiogram (ECG), Telemetry & Non-Implantable Devices for Remote Monitoring

- 12-lead ECGs will be measured in semi-supine position after 5 minutes rest (triplicate readings will be taken and averaged at all times) will be obtained at each timepoint during the study using an ECG machine that automatically calculates the heart rate and measures PR, QRS, QT, and QTcF intervals. Refer to Section [5.4.3](#) for QTcF withdrawal criteria and additional QTcF readings that may be necessary.

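### The QTcF stopping rule is written two ways: Section 5.4.1 requires attribution to the study drug, Section 5.4.3 withdraws on the threshold alone, and the two differ at exactly 530 msec

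*Protocol*

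**What the plan says.** Two sections of the protocol set QTcF limits for stopping an individual subject.

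**Section 5.4.1, item 4** covers healthy volunteers and patients without bundle branch block. The limits are above 500 msec, or for volunteers a rise of more than 60 msec from baseline. The item then adds a condition: "which is reasonably attributable to GSK3039294 on an average from triplicate readings".

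**Section 5.4.1, item 5** covers patients with bundle branch block. With a baseline below 450 msec the limit is above 500 msec. With a baseline of 450-480 msec it is "QTcF > 530 msec at any time after drug administration and is reasonably attributable to GSK3039294, as an average of triplicate readings".

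**Section 5.4.3** repeats the 500 and 60 msec limits and states: "A healthy volunteer or patient that meets either bulleted criterion below will be withdrawn from the study". It gives a separate table for bundle branch block: > 500 msec for a baseline below 450 msec, and ≥ 530 msec for a baseline of 450-480 msec. Attribution is not mentioned.

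Items 4 and 5 of 5.4.1 each refer the reader to 5.4.3. Section 7.3.5 also points to 5.4.3 "for QTcF withdrawal criteria and additional QTcF readings that may be necessary".

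**The concern.** The two sections can classify the same ECG differently. In 5.4.1 the investigator's causality judgement stands between the measurement and the stopping criterion. In 5.4.3 the measurement alone decides. No text says which prevails. If 5.4.3 prevails, the attribution conditions in 5.4.1 have no effect. If 5.4.1 prevails, the mandatory withdrawal in 5.4.3 becomes discretionary.

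This rule protects individual subjects. A site that works from 5.4.1 without following its cross-reference could go on dosing someone whose averaged QTcF is above 500 msec because the prolongation was judged unrelated.

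That judgement is a weak basis for such a decision here. Section 4.4 gives the poor precision of a causality assessment at feasible numbers as the reason for having no placebo group. Part C may also enrol patients with cardiac amyloid, in whom drug and disease effects on the ECG are hard to separate. Section 4.6.2 expects no medical benefit for any participant, so continued dosing offers the subject nothing in return.

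**Working it through.** The protocol gives no figure to reproduce on this point. The check compares the current text of the two sections.

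**Limit by limit**

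| Situation | 5.4.1 | 5.4.3 |
|---|---|---|
| No bundle branch block, absolute value | > 500 msec, if attributable | > 500 msec |
| Volunteers, change from baseline | > 60 msec, if attributable | > 60 msec |
| Bundle branch block, baseline < 450 msec | > 500 msec, attribution unclear | > 500 msec |
| Bundle branch block, baseline 450-480 msec | > 530 msec, if attributable | ≥ 530 msec |

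In item 5 the attribution phrase follows the 450-480 msec limb, after a semicolon. Whether it also covers the < 450 msec limb cannot be settled from the wording. Limits tied to attribution are therefore 3 of 4 clearly and 1 of 4 ambiguously in 5.4.1, and 0 of 4 in 5.4.3.

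**Two illustrative cases**

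- Averaged QTcF 510 msec, no bundle branch block, judged unrelated. 510 > 500, so 5.4.3 withdraws the subject. The attribution condition fails, so 5.4.1 item 4 is not met.
- Bundle branch block, baseline 450-480 msec, averaged QTcF exactly 530 msec. 530 ≥ 530 holds, so 5.4.3 discontinues. 530 > 530 is false, so 5.4.1 item 5 is not met, even if the prolongation is judged drug-related.

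**Is the attribution clause only loose drafting?** The protocol uses the same condition in the other items of 5.4.1, in the liver criteria (5.4.2) and in the renal criteria (5.4.5). It also writes unconditional triggers: under 5.4.4, sustained ventricular tachycardia or complete heart block leads to withdrawal. A reader can reasonably take both the presence of the condition in 5.4.1 and its absence in 5.4.3 as intended.

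**Averaging.** Section 5.4.3 does not mention triplicate averaging, but 7.3.5 requires it for every ECG. That is not a further conflict.

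**The pointer in 7.3.5.** It sends the reader to 5.4.3 for further QTcF readings as well as for the withdrawal criteria. Section 5.4.3 describes no such readings.

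**Context: distance from entry limit to stopping limit.** Section 5.2 excludes volunteers above 450 msec. For patients the exclusion is "Subject with mean QTcF of >480ms from a mean of triplicate readings".

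- Volunteers: 500 - 450 = 50 msec.
- Patients without bundle branch block: 500 - 480 = 20 msec.
- Bundle branch block, baseline 450-480 msec: 530 - 480 = 50 msec to 530 - 450 = 80 msec.

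These distances would be the same if the two sections agreed. They show where an exceedance is easiest to reach, not how often the sections would disagree.

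**The case against.** The strongest reply is that the sections do not order opposite actions. Section 5.4.1 lists grounds for stopping and never says that an unrelated exceedance permits further dosing. A site that obeys both sections withdraws the subject, because the broader rule contains the narrower one, and the same holds at exactly 530 msec. Both items of 5.4.1 refer to 5.4.3, 7.3.5 names 5.4.3 for QTcF withdrawal, and its title marks it as the QTc rule. Section 5.4 also lets the investigator withdraw a subject at any time for a valid clinical reason. On this view 5.4.1 merely carries redundant words.

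Much of this stands. Section 5.4.3 is the likely operative rule, and continued dosing above a limit would require a site not to follow the cross-reference. The 530 msec point is minor, and the entry margins are only context. Removing the attribution clause is also a choice that the document does not compel. The amendment history in Section 12.5 shows that item 4 was edited and its clause kept, so the clause may be deliberate.

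That last point also weakens the reply. If the clause was kept on purpose, it cannot be dismissed as redundant, and the protocol needs to say whether it applies. A cross-reference without a statement of precedence does not do that.

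**Conclusion.** The concern holds. The current text gives two QTcF stopping rules that differ on whether attribution is needed, for three of four limits clearly and for the fourth possibly. They also differ on the inequality at 530 msec. The pointer in 7.3.5 to additional readings leads to nothing.

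The practical reach is small. For Part A at 200, 600 and 1200 mg the synopsis reports: "No prolongation of the QTcF interval was observed in any subject". That evidence covers single doses in volunteers only, not repeat dosing or patients. The operator difference matters only for an average of exactly 530 msec in one subgroup. The attribution difference is the substantive part, because it decides whether withdrawal is automatic or a matter of judgement. No estimate, sample size or analysis is affected.

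The conclusion rests only on the wording of 5.4.1, 5.4.3 and 7.3.5, and on the absence of any statement of precedence. The protocol should be corrected.

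**What to change.** 1. Make Section 5.4.3 the only QTcF rule. State that withdrawal follows from the averaged triplicate QTcF regardless of attribution, with ≥ 530 msec for bundle branch block and a baseline of 450-480 msec.
2. Replace items 4 and 5 of Section 5.4.1 with a reference to 5.4.3.
3. Either describe in 5.4.3 the additional readings that 7.3.5 says are there, or delete that part of the pointer.

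If the sponsor does want attribution to count, the rule should still be stated once and the condition written into 5.4.3. The threshold-only version is preferable because it is the more cautious one.

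The cost is protocol wording, plus the occasional withdrawal of a subject whose prolongation was unrelated. Section 4.3 already allows subjects who discontinue early to be replaced.
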